#### Following the multiple-dose part in both cohorts of the study:

The following plasma PK parameters of all 3 analytes will be calculated for Day 4 and Day 8:

- Maximum plasma concentration at steady state during dosing interval (Css,max, µg/mL)
- Time to maximum concentration at steady state during dosing interval (tss,max, h), obtained directly from the observed concentration versus time data
- Minimum plasma concentration at steady state during dosing interval  $(C_{ss,min}, \mu g/mL)$
- Area under the plasma concentration-time curve from zero to time of the last quantifiable concentration  $[AUC_{(0-t)}, \mu g \cdot h/mL]$

- Area under the plasma concentration-time curve from zero to the end of the dosing interval (AUC $\tau$ , µg·h/mL), where  $\tau$  is 12 hours for Cohort 1 and 8 hours for Cohort 2
- Average plasma concentration during the dosing interval ( $C_{ss,av}$ ,  $\mu g/mL$ )
- Fluctuation index (FI, %) calculated as  $[(C_{ss,max}-C_{ss,min}) / C_{ss,av}] * 100$
- Metabolite/parent Cmax ratios of ceftaroline/ceftaroline fosamil and ceftaroline M-1/ceftaroline (RM/D,Cmax) (adjusted for differences in molecular weights)
- Metabolite/parent  $AUC_{\tau}$  ratios of ceftaroline/ceftaroline fosamil and ceftaroline M-1/ceftaroline ( $R_{M/D,AUC}$ ) (adjusted for differences in molecular weights)
- Apparent terminal rate constant ( $\lambda_z$ , 1/h)
- Terminal half-life  $(t_{\frac{1}{2}\lambda z}, h)$ , determined as  $\ln(2)/\lambda_z$
- Accumulation ratio based on  $C_{max}$  [ $R_{ac(Cmax)}$ ] calculated as  $C_{max,Day 4}/C_{max,Day 1}$  and  $C_{max,Day 8}/C_{max,Day 1}$
- Accumulation ratio based on AUC  $[R_{ac(AUC)}]$  calculated as  $AUC_{\tau,Day 4}/AUC_{(0-12),Day 1}$ and  $AUC_{\tau,Day 8}/AUC_{(0-12),Day 1}$  for Cohort 1; as  $AUC_{\tau,Day 4}/AUC_{(0-8),Day 1}$  and  $AUC_{\tau,Day 8}/AUC_{(0-8),Day 1}$  for Cohort 2
- Linearity factors calculated as  $AUC_{\tau,Day 4}/AUC_{Day 1}$  and  $AUC_{\tau,Day 8}/AUC_{Day 1}$

In addition, the following plasma PK parameters of ceftaroline and ceftaroline fosamil will be calculated for Day 4 and Day 8:

- Mean residence time (MRT, h)
- Plasma clearance at steady state (CLss for ceftaroline fosamil, apparent CLss for ceftaroline [L/h])
- Volume of distribution based on the terminal phase ( $V_z$  for ceftaroline fosamil, apparent  $V_z$  for ceftaroline [L])
- Volume of distribution at steady state (Vss for ceftaroline fosamil, apparent Vss for ceftaroline [L])

The following urine PK parameters will be calculated for Day 8:

- Amount of analyte excreted in the urine (Ae,ss, mg); the amount will be calculated for each interval and cumulatively up to the end of the dosing interval (12 hours for Cohort 1 and 8 hours for Cohort 2)
- Fraction of dose excreted into urine  $(f_{e,ss},\%)$  calculated as  $A_{e,ss}$  divided by dose for each interval and cumulatively up to the end of the dosing interval (12 hours for Cohort 1 and 8 hours for Cohort 2)
- Total fraction of dose excreted in urine  $(f_{e,ss,total},\%)$  calculated as (ceftaroline fosamil  $f_{e,ss}$ +ceftaroline  $f_{e,ss}$ +M-1  $f_{e,ss}$ ) for each interval and cumulatively
- Renal clearance (CLR,ss, L/h), calculated as cumulative Ae,ss divided by AUCτ over 12 hours for Cohort 1; and cumulative Ae,ss divided by AUCτ over 8 hours for Cohort 2

The following PK parameters from both the single- and multiple-dose parts of the study will be calculated for diagnostic purposes and listed but not summarised:

- The time interval ( $\lambda_z$  upper and lower) of the log-linear regression to determine  $\lambda_z$
- Number of data points ( $\lambda_z$ , N) included in the log-linear regression analysis to determine  $\lambda_z$ . A minimum of 3 data points will be used.
- Goodness of fit statistic for calculation of  $\lambda_z$  (Rsq). If Rsq is 0.80 or less,  $\lambda_z$  and related parameters will not be reported.
- The percent of AUC which is extrapolated to infinity (AUCex, %). If the extrapolated area ( $C_{last}/\lambda_z$ ) is greater than 20% of AUC, then AUC and related parameters will be not reported.

The linear up/log down trapezoidal summation method will be used for calculation of all areas under the curve.

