# Table 1Reported adverse events that may be related to ceftaroline (by System
Organ Class)

This information is detailed in Table 10-1 of the Investigator's Brochure.

The following is a summary of the basic pharmacokinetic (PK) properties of ceftaroline (following intravenous infusions of ceftaroline fosamil), based on in vitro and in vivo data:

- Rapid conversion of the prodrug, ceftaroline fosamil, by phosphatases to active ceftaroline in plasma
- Low human plasma protein binding (~20%) of ceftaroline with no distribution into erythrocytes
- Maximum plasma concentration (Cmax) and area under the plasma concentration-time curve (AUC) increase approximately proportionally to dose (50 to 1000 mg); with a terminal half life of 2 to 3 hours
- The prodrug ceftaroline fosamil is rapidly converted to active ceftaroline in plasma by phosphatases. Ceftaroline is further metabolised via opening of the β-lactam ring to form the microbiologically inactive metabolite M-1 and additional minor metabolites
- No inhibition or induction of cytochrome P450 (CYP) isoenzymes in vitro
- No metabolism by CYP isoenzymes in vitro
- No accumulation or time-dependent PK observed after repeated infusions every 12 hours
- Eliminated mainly through renal excretion (clearance is approximately equivalent to the glomerular filtration rate [GFR])
- Ceftaroline is not a substrate or inhibitor of human active renal uptake transporters, organic cation transporter (OCT)-2, organic anion transporter (OAT)-1, or OAT3, indicating that active secretion of ceftaroline in the kidneys does not contribute significantly to its renal elimination
- Ceftaroline is not a substrate of the efflux of transporters P-glycoprotein (P-gp) or breast cancer resistance protein (BCRP), or an inhibitor of P-gp but is a weak inhibitor of BCRP
- No effect on QTc interval
- Little effect on faecal intestinal flora
- No dose adjustment needed based on gender, age, or mild renal impairment

For further information, refer to the Investigator Brochure.

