AdministerStudy dayinvestigational product		Protocol time	PK bloo	PK urine collection b	
			Cohort 1	Cohort 2	
		8 h	X	X	Х
					I
		12 h	X	X	X
		18 h	X	X	I
2		24 h	X	X	X
	X (q12h or q8h)				
3	X (q12h or q8h)				
4		Predose a	X	X	
	X (1 st dose for q12h or q8h)	0			
		20 min	X		
		30 min		X	
		40 min	X		
		55 min	X		
		60 min		X	
		65 min	X		
		75 min	X		
		90 min	X	X	
		115 min		X	

Study day	Administer investigational product	Protocol time	PK bloo	PK urine collection b	
			Cohort 1	Cohort 2	
		120 min	X		
		125 min		X	
		2h 15 min		X	
		2.5 h		X	
		3 h	X	X	
		4 h	X	X	
		6 h	X	X	
		8 h	X	X	
	X (2 nd dose for q8h)				
		12 h	X		
	X (2 nd dose for q12h)				
	X (3 rd dose for q8h)				
5	X (q12h or q8h)				
6		Predose a	X	X	
	X (q12h or q8h)				
7	X (q12h or q8h)				
8		-2 h			X

Study day	Administer day investigational product Protocol time		PK bloo	d sample c	PK urine collection b
			Cohort 1	Cohort 2	
		Predose a	Х	X	I
	X (final dose in the morning)	0			X
		20 min	X		
		30 min		X	l
		40 min	X		l
		55 min	Х		I
		60 min		X	I
		65 min	X		I
		75 min	X		I
		90 min	X	X	I
		115 min		X	I
		120 min	X		X
		125 min		X	I
		2 h 15 min		X	I
		2.5 h		X	I
		3 h	X	X	I
		4 h	X	X	X
		6 h	X	X	I

Study day	Administer investigational product	Protocol time	PK bloo	d sample c	PK urine collection b
			Cohort 1	Cohort 2	
		8 h	X	Х	Х
					I
		12 h	X	X	X
		18 h	X	X	I
		24 h	X	X	X

h hour, min minute, PK pharmacokinetic, q12h every 12 hours, q8h every 8 hours

Cohort 1: 600 mg 1-hour infusion q12h; Cohort 2: 600 mg 2-hour infusion q8h

a On Day 1, predose plasma PK samples will be collected within 60 minutes before the start of the infusion. On Days 4, 6, and 8, predose/trough samples will be collected within 15 minutes before the start of the morning infusion.

b Subjects will be required to empty their bladders 15 minutes prior to the start of the urine sample collection and will be asked to drink 240 mL of water after bladder emptying. Urine samples will be collected on Day 1 and Day 8 at the following intervals: -2 to 0 hours, 0-2 hours, 2-4 hours, 4-8 hours, 8-12 hours and 12-24 hours.

C PK samples times are from the start of the infusion

Additional assessment or sampling times may be added. However, the maximum blood volume taken from each subject will not exceed 450 mL.

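### Day 4 half-life of metabolite M-1 is required from samples that stop at the next dose; in the 8-hourly cohort it comes out too long, and the Rsq rule does not catch it

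*Protocol*

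**What the plan says.** Section 10.2 (multiple-dose part) says "The following plasma PK parameters of all 3 analytes will be calculated for Day 4 and Day 8". The list under that line contains the apparent terminal rate constant and terminal half-life, so both are due for M-1 on Day 4. The synopsis repeats this. A second list follows: "In addition, the following plasma PK parameters of ceftaroline and ceftaroline fosamil will be calculated for Day 4 and Day 8". It holds MRT, steady-state clearance, Vz and Vss, and leaves M-1 out.

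The dosing interval "is 12 hours for Cohort 1 and 8 hours for Cohort 2". In the sampling schedule (Figure 3, Section 3.1) the last Day 4 sample in Cohort 2 is at 8 h, followed by the row "X (2 nd dose for q8h"). In Cohort 1 it is at 12 h, again followed by a dose. Day 8 carries "X (final dose in the morning") and both cohorts are then sampled to 24 h.

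Three reporting guards close Section 10.2:
- On the number of points: "A minimum of 3 data points will be used".
- The rate constant and what depends on it are dropped when Rsq is 0.80 or below.
- If the extrapolated area "is greater than 20% of AUC, then AUC and related parameters will be not reported".

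Section 1.1 describes ceftaroline "with a terminal half life of 2 to 3 hours" and says M-1 is formed from it by ring opening. No half-life for M-1 is given anywhere.

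**The concern.** A terminal half-life is meaningful only if the fitted points lie in the log-linear terminal phase. In Cohort 2 the infusion takes 2 h of an 8 h interval, which leaves 6 h, or 2 to 3 ceftaroline half-lives. That may serve for ceftaroline. It is short for M-1, whose curve lags behind the parent because it is still being formed while ceftaroline falls.

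The secondary objective is to characterise single- and multiple-dose PK of all three analytes under the two regimens, and Section 11.2.4 presents parameters by analyte, cohort and study day. A half-life that is too long on Day 4 only, and more so in Cohort 2, would read as a change in M-1 elimination with time or regimen.

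**Working it through.** There is no stated M-1 figure to reproduce, so the check asks what the prescribed fit would return.

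**Inputs from the protocol.** Infusion length T is 1 h (Cohort 1) or 2 h (Cohort 2). The interval is 12 h or 8 h. There is one dose on Day 1, then repeated dosing from Day 2. Day 4 starts at 72 h and Day 8 at 168 h. The last three Day 4 samples are at 6, 8, 12 h (Cohort 1) or 4, 6, 8 h (Cohort 2). The last three Day 8 samples are at 12, 18, 24 h. Ceftaroline half-life is 2 to 3 h.

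**Assumptions.** Kinetics are linear, prodrug conversion is immediate, ceftaroline is one-compartment, and M-1 half-life is 1 to 6 h. The fit uses the last three points, which is the latest window the three-point minimum allows.

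**Model.** With rate constants kp (ceftaroline) and km (M-1), each ln 2 divided by the half-life, one infusion gives, up to a scale factor,

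M(t) = kp/(km − kp) × [g(t; kp) − g(t; km)],

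where g(t; k) = (1 − e^(−kt))/k during the infusion and (e^(−k(t−T)) − e^(−kt))/k afterwards. Doses are summed. Half-life is ln 2 divided by the negative slope of log M on time.

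**One case in full** (Cohort 2, ceftaroline 3 h, M-1 4 h; M-1 as a percentage of its 4 h value on Day 4):
- Day 4: 97.5 at 3 h, 100.0 at 4 h, 94.0 at 6 h, 81.2 at 8 h. The points at 4, 6, 8 h are equally spaced, so the slope is ln(0.812)/4 = −0.0521 per h and the half-life is 0.693/0.0521 = 13.3 h. Rsq is 0.95.
- Day 8: 52.98 at 12 h and 9.60 at 24 h. The slope is −ln(52.98/9.60)/12 = −0.1423 per h and the half-life is 4.87 h.
- Ratio: 13.3/4.87 = 2.7.

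**Across the range:**

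| Ceftaroline / M-1 half-life (h) | Cohort 2 Day 4 (h) | Rsq | Cohort 2 Day 8 (h) | Ratio, Cohort 2 | Ratio, Cohort 1 |
|---|---|---|---|---|---|
| 2 / 1 | 2.66 | 0.99 | 2.01 | 1.32 | 1.06 |
| 2 / 4 | 8.94 | 0.97 | 4.23 | 2.11 | 1.30 |
| 2 / 6 | 13.58 | 0.96 | 6.22 | 2.18 | 1.30 |
| 2.5 / 4 | 11.08 | 0.96 | 4.51 | 2.46 | 1.41 |
| 3 / 1 | 3.94 | 0.99 | 3.01 | 1.31 | 1.05 |
| 3 / 4 | 13.31 | 0.95 | 4.87 | 2.73 | 1.50 |
| 3 / 6 | 20.39 | 0.93 | 6.86 | 2.97 | 1.55 |

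A prodrug half-life of 0.05 h instead of immediate conversion changes little: the last row becomes 3.08 and 1.57. The Day 8 value is itself close to the true terminal half-life, at 1.00 to 1.31 times.

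**The guards.** Rsq exceeds 0.90 in every row. With 5% log-normal noise, 53 to 94% of Cohort 2 profiles still pass 0.80, and with 10% noise 34 to 74% do (M-1 half-life 3.1 to 6 h). Among those passing, the median estimate is 1.7 to 3.3 times the true value. The extrapolation rule would nearly always be breached for M-1 in Cohort 2 (19 to 85% extrapolated), but it withholds AUC and its dependants, and half-life is computed from the rate constant.

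**Ceftaroline, for comparison.** A one-compartment parent returns half-life, Vz and Vss exactly on Day 4. Two-compartment cases in Cohort 2 give half-life and Vz at 0.73 to 0.92 of true and Vss at 0.92 to 0.97.

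**The case against.** The best defence is that the protocol does not force the 4, 6, 8 h fit. Parameters are due only where possible, standard procedures not shown here are the default where the protocol is silent, and the text does not say whether the Cmax point may enter the regression. In 86% of the modelled Cohort 2 cases the sampled M-1 maximum is at 4 h. If that point is excluded, two remain and the three-point minimum blocks the estimate. This stands in part: the result is then missing instead of too long. Neither outcome is useful, and a qualifier without a criterion does not rule out a three-point fit with Rsq near 0.95.

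It is also fair that nothing is tested, M-1 is microbiologically inactive, steady state is judged from troughs, accumulation uses Cmax and AUC ratios, and the fit interval, number of points and Rsq are listed. This limits the consequence. It does not make the tabulated value right.

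A reader might infer that every Day 4 terminal-phase parameter is wrong. The documents do not support that. MRT, Vz and Vss are not derived for M-1. For ceftaroline the effect is nil or modest and in the opposite direction, and no error is shown for the prodrug.

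A reader might also infer that the 20% rule would selectively remove slow eliminators of ceftaroline in Cohort 2. In the one-compartment model the extrapolated share there is 9, 14 and 19% at half-lives of 2, 2.5 and 3 h, and reaches 20% only at 3.08 h, above the stated range. A count of subjects lost needs an assumed between-subject spread. It also assumes that the rule reaches Day 4 MRT and Vss, although AUC to infinity is listed only for Day 1.

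**Conclusion.** The point holds for M-1 rate constant and half-life on Day 4, mainly in Cohort 2. The fitted half-life is roughly 1.3 to 3 times the Day 8 value there and about 1.05 to 1.55 times in Cohort 1, and the Rsq rule does not screen it out.

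These factors rest on a linear model and an assumed M-1 half-life of 1 to 6 h. They are neither protocol figures nor bounds. Measured against the true terminal half-life, over a wider grid (M-1 1 to 8 h, prodrug 0.005 to 0.2 h), the Cohort 2 ratio runs from 1.3 to 4.2. The direction is the same throughout. It would be too strong to say that the value passes all the plan's quality rules: only the Rsq rule is shown to be passed, and the three-point minimum may leave no estimate.

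The consequence is a possible false impression of time- or regimen-dependent M-1 elimination in descriptive secondary results. Days 1 and 8 still give usable half-lives.

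**What to change.** In the multiple-dose list of Section 10.2 and the matching synopsis paragraph, limit M-1 terminal rate constant and half-life to Day 8, and leave the Day 1 entries as they are. Keep the Day 4 parameters that need only one dosing interval: Cmax, tmax, Cmin, AUC over the interval, average concentration, fluctuation, and the ratios.

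Optionally, for simpler tables, take ceftaroline half-life, MRT, Vz and Vss from Days 1 and 8 as well. The calculations do not require this.

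The cost is a wording change in two places and the loss of a Day 4 M-1 half-life, which Day 8 supplies with sampling to 24 h. No sample, visit or subject changes.

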# 11. STATISTICAL METHODS AND SAMPLE SIZE DETERMINATION

## **11.1 Description of analysis sets**

#### 11.1.1 General principles

The analysis of data will be based on different subsets according to the purpose of analysis, ie, for safety and PK, respectively. The decision regarding validity of data for each of the analysis sets will be based on a blind review of data.

The as-treated principle will be applied to all evaluations; ie, subjects who received a treatment other than the one assigned in the randomisation list will be analysed as belonging to the actual treatment group and not that assigned by randomisation.

#### 11.1.2 Safety analysis set

All subjects who received at least one dose of randomised investigational product, and for whom any post-dose data are available will be included in the safety analysis set.

## 11.1.3 PK analysis set

The PK analysis set will include all subjects who received at least 1 dose of ceftaroline fosamil and have at least 1 measured concentration of any of the 3 analytes in plasma or urine at a scheduled time point after the start of the infusion. The PK analysis set should include all evaluable data appropriate for the evaluation of interest (with no major protocol deviations, violations, or events thought to significantly affect the PK of the investigational product) from all subjects who receive investigational product.

# **11.2** Methods of statistical analyses

## **11.2.1** General principles

Data will be presented by actual dose (not by cohort), and subjects receiving placebo will be pooled across dosing cohorts for the purposes of summarising the safety results.

Given the exploratory nature, no formal statistical hypothesis testing will be performed in this study. Since no planned formal testing will be performed in this study, and the confidence intervals that will be calculated are only for descriptive purposes, no corrections for multiplicity will be used.

Missing data will result in a reduced sample size for that parameter. Since the statistical analyses will be predominantly presentations in tables and individual data listings, no action will be taken to handle missing data.

A subject who withdraws prior to the last planned observation in a study period will be included in the analyses up to the time of discontinuation.

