## 3.1 Overall study design and flow chart

This is a Phase I, randomised, double-blind, placebo-controlled, parallel group study in healthy male and female subjects conducted at a single study centre. Up to 40 healthy subjects aged 18 to 55 years (inclusive) will participate in 2 cohorts. Each cohort will be divided into 4 subgroups of 5 subjects each.

Twenty subjects will participate in each cohort and will receive either ceftaroline fosamil (15 subjects) or placebo (5 subjects). Each subject will only participate in 1 cohort. The dose will be 600 mg 12-hourly (infused over 1 hour) in Cohort 1 and 600 mg 8-hourly (infused over 2 hours) in Cohort 2.

[figure not shown]
After a screening period of up to 28 days, subjects will be admitted to the study centre on Day -1, discharged on Day 9 and followed up 7 to 10 days after discharge (see Figure 1).

On Days 1 and 8 subjects will receive a single dose of 600 mg ceftaroline fosamil or placebo.

Repeated infusions will commence on Day 2. Subjects will then receive ceftaroline fosamil or placebo every 12 hours (Cohort 1) or every 8 hours (Cohort 2) from Days 2 to 7. It is anticipated that this will be sufficient to achieve and maintain steady state for several days and evaluate the safety of multiple infusions adequate for the intended target. Throughout the residential period there will be safety monitoring and serial blood samples for PK evaluation (for details see Figure 3).

Local tolerability will be assessed according to the VIP scale. The VIP score will be recorded for all local reactions; any local reaction with a VIP score of 2 or greater will be determined as an ISR and will be recorded as an adverse event. See Section 6.3.1.

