#### 5.5.2 Doses and treatment regimens

Each subject will receive a single infusion of ceftaroline fosamil or placebo on the morning of Day 1 and Day 8.

Repeated infusions will start on Day 2 and continue through Day 7. Ceftaroline fosamil (600 mg) or placebo will be administered every 12 hours over 1 hour to subjects in Cohort 1 (total daily dose 1200 mg) and every 8 hours over 2 hours to subjects in Cohort 2 (total daily dose 1800 mg).

On Days 1 and 8, subjects will be required to empty their bladders 15 minutes prior to the start of the PK urine sample collections and will be asked to drink 240 mL of water after bladder emptying.

After the investigational product administration, subjects will remain on their beds or sitting for as long as necessary for the required study procedures.

Subjects will fast from 1 hour before to 1 hour after the end of the infusion.

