## 11.2.4 Pharmacokinetics

Individual PK blood and urine sample collection times, as well as derived sampling time deviations, and concentration-time data will be listed. Individual plasma concentration-time profiles of the 3 analytes will be depicted on linear and semi-logarithmic scales.

Pharmacokinetic data will be presented by analyte, cohort, and study day as appropriate.

Plasma concentrations will be summarised by nominal time points using descriptive statistics including: the population size (N for sample size and n for available data), geometric mean, geometric coefficient of variation (CV%), arithmetic mean, SD, median, min, and max.

The geometric mean is calculated as the exponential of the arithmetic mean calculated from data on a log scale. The CV% is calculated as  $100 \cdot \sqrt{(\exp(s^2) - 1)}$  where *s* is the SD of the data on a log scale.

Plasma concentrations that are below the lower limit of quantification (LLOQ) will be handled as follows:

- At a time point where less than or equal to 50% of the values are below the LLOQ (BLQ), all BLQ values will be set to LLOQ, and all descriptive statistics will be calculated
- At a time point where more than half of the values are BLQ, the mean, SD, geometric mean, and CV% will be set to Not Determined (ND). The max value will be reported from the individual data, and the min and median will be set to BLQ
- If all values are BLQ at a time point, no descriptive statistics will be calculated for that time point. Not applicable (NA) will be written in the field for SD and CV% and BLQ will be written in fields for mean, geometric mean, min, median, and max
- The number of BLQ values (n below LLOQ) will be reported for each time point

Plasma and urine PK parameters will be summarised by analyte, cohort, and/or study day as appropriate using descriptive statistics including: N, n, geometric mean, CV%, arithmetic mean, SD, median, min, and max.

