#### Visual assessments of steady state

Mean (±SD) and individual predose/trough concentration-time profiles of each analyte during the multiple-dose period will be presented by dose group for visual assessments of steady state.

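### Section 11.2.1 groups data by actual dose and not by cohort, but both cohorts receive 600 mg per infusion, so read literally the rule merges the two regimens in the safety summaries

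*Protocol*

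**What the plan says.** The general rule in Section 11.2.1 reads: "Data will be presented by actual dose (not by cohort"). The same sentence pools placebo subjects across the two cohorts and ends by tying the pooling to the summary of safety results.

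Section 3.1 sets out the regimens: "The dose will be 600 mg 12-hourly (infused over 1 hour) in Cohort 1 and 600 mg 8-hourly (infused over 2 hours) in Cohort 2". It adds: "On Days 1 and 8 subjects will receive a single dose of 600 mg ceftaroline fosamil or placebo". For Days 2 to 7, Section 5.5.2 gives the Cohort 1 schedule as "every 12 hours over 1 hour to subjects in Cohort 1 (total daily dose 1200 mg"); the matching figure for Cohort 2, dosed every 8 hours over 2 hours, is 1800 mg.

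Sections 11.2.2 and 11.2.3 summarise subject characteristics and safety by treatment group, without defining the term. Section 11.2.4 uses a different grouping: "Pharmacokinetic data will be presented by analyte, cohort, and study day as appropriate". Its closing paragraph on steady state changes the label again: trough profiles "will be presented by dose group for visual assessments of steady state".

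**The concern.** A rule to present by dose and not by cohort works when cohorts receive different doses. Here the milligram amount per infusion is the same in both, and what distinguishes the regimens is interval and infusion length, for which cohort is the protocol's only short label. The sentence names the wrong grouping variable and expressly sets aside the right one.

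The primary objective (Section 2.1) is the safety and tolerability of different dose regimens against placebo. Section 1.2 says the 8-hourly 2-hour regimen needs evaluating against the approved 12-hourly 1-hour regimen for safety, tolerability and pharmacokinetics, in support of Phase III. A single active column would blur an adverse-event excess confined to one regimen. It would also make an absence of events look better supported than it is for either regimen. Infusion-site tolerability, assessed under Section 6.3.1, is an obvious place for regimens with different infusion times to diverge.

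**Working it through.** **Inputs.** 600 mg per active infusion in both cohorts (Sections 3.1 and 5.5.2); one infusion on each of Days 1 and 8; two per day (Cohort 1) or three per day (Cohort 2) on the six days from Day 2 to Day 7; infusion length 1 h or 2 h; 15 active and 5 placebo subjects per cohort (Section 5.2.1).

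**The plan's own figures.** 2 × 600 = 1200 mg/day and 3 × 600 = 1800 mg/day, as Section 5.5.2 states. The protocol gives no power or formal sample size to reproduce.

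**Planned exposure per active subject.** Infusions = 1 + 6k + 1, where k is the number per day on Days 2 to 7.
- Cohort 1: 1 + 12 + 1 = 14 infusions; 14 × 600 = 8400 mg; 14 × 1 h = 14 h.
- Cohort 2: 1 + 18 + 1 = 20 infusions; 20 × 600 = 12000 mg; 20 × 2 h = 40 h.

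**Columns under each reading of dose.**

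| Reading | Active columns | Placebo (pooled) |
|---|---|---|
| mg per infusion | 15 + 15 = 30 in one column | 5 + 5 = 10 |
| Total daily dose, Days 2 to 7 | 15 (1200 mg), 15 (1800 mg) | 10 |
| Total daily dose, Days 1 and 8 | 30 in one column (600 mg each) | 10 |
| Regimen | 15 (q12h, 1 h), 15 (q8h, 2 h) | 10 |

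Only the regimen reading separates the cohorts on every study day.

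**What merging does to a descriptive table.**
- No events observed: the exact one-sided 95% upper bound is 1 − 0.05^(1/n). For n = 30 it is 9.5%; for n = 15 it is 18.1%. A merged column would suggest about twice the reassurance available for either regimen.
- Some events observed: with equal group sizes the merged rate is the simple average. The documents give no regimen-specific adverse-event rates, so these are assumptions: 0% and 20% would show as 10%; 5% and 20% as 12.5%; 5% and 30% as 17.5%.

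**The case against.** The strongest reply is that dose here means regimen. The synopsis says 12 subjects suffice to characterise each dose, and its target is 12 completers out of 15 active subjects per cohort, so each dose must there mean each cohort's regimen. Section 5.4.1 describes blinding at each dose level, which implies more than one level. On that reading, setting cohort aside means only that each cohort's placebo subjects do not get their own column, which fits the pooling in the same sentence and the as-treated principle in Section 11.1.1. The result would be 15, 15 and 10.

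This is plausible, and it stands as a likely account of intent. It is not what the sentence says. Elsewhere the protocol writes dose regimen when it means that (Sections 1.2, 2.1 and 3.2). Treatment group does not restore the split either, because the nearest uses of treatment are binary: Sections 5.2.1 and 5.4.1 both speak of ceftaroline fosamil or placebo.

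The reply is stronger for pharmacokinetics. A reader might infer that trough plots will average 12-hour and 8-hour troughs. The regimens' troughs should indeed differ. Take a one-compartment model with Section 3.2's predicted AUCs (67.1 and 70 µg·h/mL, assumed to be per dosing interval) and rate constant k = ln 2 / half-life. With infusion length T and interval τ, the trough is (AUC/T)(1 − e^(−kT)) e^(−k(τ−T)) / (1 − e^(−kτ)). At a half-life of 2.5 h this gives 0.80 and 3.17 µg/mL; across the stated 2 to 3 h range the ratio runs from about 5.3 to 3.3. But the documents do not direct that average. Section 11.2.4 is the specific rule and presents by cohort, the steady-state paragraph sits under it, and individual profiles are plotted as well as means.

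A reader might also infer that the safety results could never be shown by regimen. That too goes beyond the text: Section 11.2.1 mentions individual listings, and the same data could be re-tabulated. The study is descriptive, so no test or error rate is affected. The SAP is not at hand and may define the columns. The point is still not one of missing detail: the protocol states a rule, and a SAP that followed it literally would carry the error forward.

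**Conclusion.** The point holds for safety and subject characteristics. Taken at its word, Section 11.2.1 gives 30 active and 10 placebo subjects where the primary objective calls for 15, 15 and 10, and merges planned exposures of 8400 mg over 14 h and 12000 mg over 40 h. This rests on reading dose as the amount per infusion, the sense in which Section 3.1 states it for Days 1 and 8. Total daily dose rescues the rule only for Days 2 to 7.

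For pharmacokinetics the defect is smaller: Section 11.2.1 conflicts with Section 11.2.4, and dose group is used loosely in the steady-state paragraph. If the closing words of the Section 11.2.1 sentence are taken to confine all of it to safety, that conflict disappears, but the rule then falls wholly on the primary objective.

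The documented consequence is the change in columns. How far it would mask a real difference depends on event rates that the documents do not give.

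**What to change.** Replace the first clauses of Section 11.2.1 with: *Data will be presented by regimen actually received (ceftaroline fosamil 600 mg q12h over 1 h; ceftaroline fosamil 600 mg q8h over 2 h; placebo pooled across cohorts for safety).* Define treatment group in Sections 11.2.2 and 11.2.3, and dose group in the steady-state paragraph, in the same way, so that Sections 11.2.1 and 11.2.4 agree. Carry the definition into the SAP and table shells.

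The cost is wording only. Dosing, randomisation, sample size and data collection do not change, and the pooling of placebo for safety is kept as planned.
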